Official title: Mindfulness-Based Intervention for Caregivers of Frail older adults:
Towards a model of intergenerational caregiving for Chinese families

NCT number: to be assigned

Document date: April 22, 2021

The research questions of the proposed study are:

- 1) investigate the effects of a brief mindfulness-based intervention for caregivers of frail elders in reducing caregiver burden and depression;
- 2) compare the effects of mindfulness-based intervention with an evidence-based caregiver programme; and
- 3) explore the factors that contribute to the positive improvements of both caregiver programmes, and develop a preliminary model for understanding and reducing caregiver burden and depression.

RESEARCH PLAN AND METHODOLOGY

Study design

In view of the research objectives about efficacy of the MBI and in the interest of developing a model of mediators in the MBI and intergenerational caregiving, a multi-site, three-arm, randomized controlled trial will be implemented (Baron et al., 2013). The effects of the MBI for caregivers for frail elderly will be tested by comparing the MBI (Arm 1), with psychoeducation (Arm 2), and treatment-as-usual (Arm 3). Assessments will be scheduled pre-intervention (T0), post-intervention (T1), and at 6-month follow-up (T2). The program effects will be tested using both pairwise between-subject comparisons (Arm 1 vs Arm 2, Arm 2 vs Arm 3, and Arm 1 vs Arm 3) and within-subject comparisons (measures at T0, T1, and T2). The between-group analyses will be adjusted for baseline scores and for factors related to outcomes, including the age and sex of the caregivers, the severity of depression, anxiety, caregiver burden, and the level of frailty of elderly. Refinement of design from a pilot study. A pilot study has been conducted in August to September 2019.

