Sample size estimation. We calculated the sample size needed for the first two hypotheses and choose the larger one for the estimation of overall sample size. For the first hypothesis, the calculation is based on a previous study of an MBI for caregivers (Hou et al., 2014), in which an effect size of 0.64 in depression, with an estimation of an effect size of 0.14 for Arm 3. For a two-tailed α error of 5%, an 80% power, and a test of three independent groups, the required sample size will be 64 per arm (Cohen, 1988). For the second hypothesis, the calculation is based on a non-inferiority comparison was conducted. A non-inferiority margin of 50%, as common practice in non-inferiority trials (Althunian et al., 2017), is selected and the required sample size will be 51 per arm. We further adjust the sample size based on an estimation of drop-out rate and intra-class correlation. An estimation of a drop-out rate of 15% is based on two local studies of mindfulness-based intervention (Hou et al., 2014; Lo et al.,

2015). Besides, an estimation of intra-class correlations of 0.07 is based on PI's two recent mindfulness multi-site studies ranged from 0 to 0.07 (Lo et al., 2017; Lo et al., in press), and 240 caregivers will be recruited for this study. Based on such estimation, it should also be necessary to conduct mediational studies with .8 statistical power (Fritz & MacKinnon, 2007).

Recruitment of participants. The inclusion criteria for participation in this study are: 1) Caregivers of frail elderly based on a professional's assessment of Clinical Frailty Scale with a score of 6, indicating a moderate level of frailty or above (Rockwood et al., 2005). 2) Caregivers being adult children or children in-law of the elder care receiver. 3) Caregivers who are experiencing caregiver burden at the time of study, with scores of 8 or above in ZBI-4 (Bedard et al., 2001). The exclusion criteria include: 1) Caregivers who have diagnoses of psychosis, developmental disabilities, or cognitive impairment, which may present difficulties in comprehending the content of the program. 2) Spouses, siblings, or friends will be excluded as their burden or depressive symptoms may be attributed to different reasons. 3) Caregivers of elders with moderate to severe dementia will be excluded and the Clinical Dementia Rating Scale will be administered (Huges et al., 1982), and 4) Caregivers who had participated in a MBSR or equivalent.

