All analyses will be carried out according to the intention-to-treat approach and all participants who receive randomization and allocation to one of three treatment arms will be included for analyses (Moher et al., 2010). Repeated measure ANOVA will be used to evaluate the effects of the MBI (Arm 1), relative to PSY (Arm 2) and TAU (Arm 3), and the analyses of the primary and secondary outcome measures will be analyzed. In addition to the immediate programme effects, outcomes measured at T1 and T2 will be compared, to assess whether maintenance effects will be sustained at 6-months.

The mediation effects on the relationships between group (MBI or PSY vs. TAU)

variables and caregiver outcome variables (ZBI, CES-D, HAD-A), controlling the baseline variables (sex and age of caregivers, frailty score), will be evaluated using the PROCESS macro in SPSS (Hayes, 2012), in order to compute the effect of the independent variable on the mediator (a), the effect of the mediator on the dependent variable (b), total effect (c), direct effect (c'), and bootstrapped (i.e., 10,000 random samples) bias-corrected 95% confidence intervals of the indirect effect (ab).

According to Hayes (2009), with significant paths a and b, even without a significant path c, confidence intervals that do not include zero indicate a significant indirect (i.e., mediation) effect.

Appendix 1
Recruitment Flowchart

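### The 64 per arm is the two-group size for MBI versus usual care at a difference of 0.50 SD, not the size for the three-group test to which the plan attributes it

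*Combined protocol and SAP*

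**What the plan says.** Sample size estimation sizes two hypotheses and keeps the larger figure. For the first it takes "an effect size of 0.64 in depression, with an estimation of an effect size of 0.14 for Arm 3". It then sets the error rates ("For a two-tailed α error of 5%, an 80% power"), names the test and gives the size: "a test of three independent groups, the required sample size will be 64 per arm". It states no Arm 2 effect, no three-group effect measure and no multiplicity rule for this calculation.

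The second hypothesis, a non-inferiority comparison, is sized at 51 per arm. The larger figure, 64, is then adjusted for drop-out and intra-class correlation, and the plan arrives at 240 caregivers.

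Two other sections bear on which test the power should describe. Study design commits to "pairwise between-subject comparisons (Arm 1 vs Arm 2, Arm 2 vs Arm 3, and Arm 1 vs Arm 3". Data Analyses says "Repeated measure ANOVA will be used to evaluate the effects of the MBI (Arm 1), relative to PSY (Arm 2) and TAU (Arm 3".

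**The concern.** A power figure belongs to a particular test under particular assumptions. The plan names a three-group test but supplies means for only two groups, and a three-group F test cannot be sized from two means. The two-tailed error rate also suits a t-test, since an omnibus F test has no tails in that sense.

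The figure matters because 64 is the base for the 240. A reader who takes the label literally could believe that the three-arm analysis has 80% power. The stated inputs show that power only for MBI versus usual care, without adjustment for multiple comparisons. Arm 2 versus Arm 3 is one of the three listed pairwise comparisons, yet it has neither an assumed effect nor a stated power. A null result there could be misread as coming from a contrast designed with 80% power.

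**Working it through.** **Inputs from Sample size estimation.** Effects 0.64 (Arm 1) and 0.14 (Arm 3), in SD units, so SD = 1; two-sided α = 0.05; power 80%; 64 per arm.

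**Assumptions made here.** The difference 0.64 − 0.14 = 0.50 is our subtraction; the plan does not write it. Equal allocation is inferred from the single per-arm figure. The Arm 2 effect x is not given and is varied from 0.14 to 0.64.

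**Step 1: reproduce 64 as a two-group test.** The two-sample t-test with n per arm has 2n − 2 degrees of freedom and noncentrality d√(n/2).
- n = 64, d = 0.50: noncentrality 0.50 × √32 = 2.83, 126 degrees of freedom, power 0.801.
- n = 63: power 0.795.

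The smallest n that reaches 80% is 64, exactly the plan's figure. As corroboration, the one-sided 5% two-group t-test at 0.50 needs 51 per arm, which is the plan's figure for the second hypothesis. Both sizes therefore match two-group calculations at the same difference.

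**Step 2: size the test the plan names.** The one-way F test with three groups has 2 and 3(n − 1) degrees of freedom and noncentrality λ = n × Σ(mean − grand mean)². The means are 0.64, x and 0.14.

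Worked case, x = 0.39: the grand mean is 0.39 and the squared deviations sum to 0.25² + 0² + 0.25² = 0.125. At n = 64, λ = 64 × 0.125 = 8.0 and power is 0.710.

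| Arm 2 effect x | n per arm for 80% | Power at 64 per arm |
|---|---|---|
| 0.14 or 0.64 | 59 | 0.835 |
| 0.18 or 0.60 | 64 | 0.804 |
| 0.20 or 0.58 | 66 | 0.789 |
| 0.25 | 71 | 0.756 |
| 0.30 | 75 | 0.730 |
| 0.39 (midway) | 79 | 0.710 |

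The paired values follow from symmetry about 0.39. Power at 64 is at least 0.80 only when x is about 0.14–0.18 or 0.60–0.64.

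**Step 3: Arm 2 versus Arm 3.** The two-group formula at 64 per arm, unadjusted, for assumed differences:
- 0.25 SD: power 0.29
- 0.40 SD: power 0.61
- 0.50 SD: power 0.80

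**Step 4: what these figures leave out.** Steps 1 to 3 ignore drop-out and intra-class correlation, which lower power. If the 240 are split equally, 80 per arm × 0.85 = 68 remain after 15% drop-out. F-test power at 68 is then 0.738 (Arm 2 midway) to 0.858 (Arm 2 equal to another arm), before any clustering effect. Baseline adjustment, planned under Study design, may raise power, but the plan gives no correlation. As an illustration only: if 0.50 is in raw SD units and baseline adjustment shrinks the SD by √(1 − r²), F-test power at 64 with Arm 2 midway is 0.75, 0.81 and 0.83 for r = 0.3, 0.44 and 0.5.

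**The case against.** The strongest reply is that the number is sound and only its label is wrong. The first research question asks about the effects of the MBI, and the effects supplied are those of MBI and Arm 3, so a comparison of Arm 1 with Arm 3 is the natural reading. The mention of three groups may only describe the design. This stands, and the fix follows it.

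The low-power cases also need psychoeducation to be clearly weaker than MBI. The plan calls Arm 2 an evidence-based programme and tests non-inferiority against it, which fits better with active arms that are about equal. If Arm 2 is at 0.64, the F test needs 59, so 64 is enough (0.835), and Arm 2 versus Arm 3 differs by 0.50 with power 0.80. This also stands as a plausible scenario, but the plan does not state it as an assumption, and a calculation cannot rest on an unstated one.

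Baseline adjustment could close the gap, as Step 4 shows, but no correlation is given to credit it.

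Three stronger readings are tempting, and the documents do not support them. First, a reader might infer that the trial is underpowered. It is not shown to be: 64 gives 80% for Arm 1 versus Arm 3, and whether the F test falls short depends on an Arm 2 effect that nobody has stated. Second, a reader might infer that no three-group calculation could yield 64. One does, with Arm 2 at 0.18 or 0.60. Third, a reader might infer that every contrast except Arm 1 versus Arm 3 went unsized. The non-inferiority hypothesis is sized separately, at 51 per arm.

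**Conclusion.** The stated inputs cannot produce the stated power for the stated test. They reproduce 64 per arm exactly for a two-sided, unadjusted comparison of MBI with usual care at 0.50 SD. For the three-group F test, the required size is 59 to 79 per arm and the power at 64 is 0.71 to 0.835, depending on an Arm 2 effect assumed to lie between the other two. It reaches 0.80 only if Arm 2 is within about 0.04 of one of them. Arm 2 versus Arm 3 is planned without any stated assumption or power.

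The conclusion rests on the subtraction that gives 0.50, on equal allocation, and on simple two-group and one-way models rather than the planned repeated-measures analysis. The exact match at 64, together with the match at 51, makes the two-group origin very likely, though the plan does not confirm it. This is a mislabelled power statement that should be corrected, and no more than that.

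**What to change.** In Sample size estimation, replace the reference to a three-group test with wording such as: *the two-group comparison of MBI (Arm 1) with TAU (Arm 3), difference 0.50 SD, unadjusted two-sided 5%*.

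Then do one of two things:
- state the assumed Arm 2 effect, and give the resulting power for the three-arm test and for Arm 2 versus Arm 3; or
- state that no 80% power is claimed for either.

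The cost is two sentences and a narrower power claim. Enrolment and trial conduct do not change.

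### Hypothesis 2 is sized as a non-inferiority comparison, but the planned analysis never tests against a margin and the 50% margin has no stated base

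*Combined protocol and SAP*

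**What the plan says.** Under Sample size estimation the combined protocol and SAP states: "We calculated the sample size needed for the first two hypotheses". The larger result is then carried forward.

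- **Hypothesis 1.** The inputs are "an effect size of 0.64 in depression, with an estimation of an effect size of 0.14 for Arm 3". With a two-tailed 5% error, "an 80% power, and a test of three independent groups, the required sample size will be 64 per arm".
- **Hypothesis 2.** "For the second hypothesis, the calculation is based on a non-inferiority comparison was conducted". The margin is given as "A non-inferiority margin of 50%, as common practice in non-inferiority trials", and it "is selected and the required sample size will be 51 per arm". No alpha, sidedness, power, outcome, reference effect or expected difference is given for this calculation.

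The hypotheses are not listed. The second is taken to be research question 2: "compare the effects of mindfulness-based intervention with an evidence-based caregiver programme".

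Study design plans pairwise between-arm comparisons, adjusted for baseline scores and other factors, and within-subject comparisons over T0, T1 and T2. Data Analyses plans repeated-measures ANOVA under intention-to-treat. Non-inferiority is mentioned only in the sample size section. Table 1 makes caregiver burden (ZBI) the primary outcome; depression is secondary.

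**The concern.** A non-inferiority claim needs a margin fixed in advance and a confidence limit that lies inside it. The plan has neither in usable form. The pairwise comparisons and the ANOVA test for a difference, and failing to find one does not show that MBI is no worse than psychoeducation by more than a tolerable amount. One of the two hypotheses used for sizing therefore has no matching test.

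The margin cannot be recovered from the text either. Half of an effect means something only once the effect is named, and no psychoeducation effect appears anywhere. The Procedures section describes the comparator as a dementia-caregiver programme still to be modified for frail elders, so an effect cannot be carried over without argument. The 0.64 is for depression, not for the primary outcome.

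At stake is whether the MBI versus psychoeducation result can be interpreted.

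**Working it through.** **Method.** Two equal arms, SD = 1, one time point, two-sample t-test power. For non-inferiority the distance is D = margin + true MBI advantage. The normal approximation is n per arm = 2(z_alpha + z_power)² / D²; the t solution adds about one per arm.

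**Step 1: hypothesis 1.** Net effect 0.64 - 0.14 = 0.50, two-sided 5%, 80% power: 2(1.960 + 0.842)² / 0.50² = 62.8; t solution 63.77, so 64. The stated figure is reproduced.

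**Step 2: hypothesis 2.** Margin 0.50 SD, zero true difference, one-sided 5%, 80% power: 2(1.645 + 0.842)² / 0.50² = 49.5; t solution 50.15, so 51. This is the simplest reading that gives the stated figure, but it is an inference. Its margin equals the whole net MBI effect in step 1, so it would preserve none of a psychoeducation effect of similar size. For 0.50 SD to be half of the psychoeducation effect, that effect would have to be about 1.0 SD.

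Other inputs also give 51. At one-sided 2.5% the matching margin is about 0.56 SD. At one-sided 5%, a margin of 0.25 SD matches if MBI is truly better by about 0.25 SD. So 51 does not identify the margin.

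**Step 3: margin as half of an assumed effect.** Assume a psychoeducation effect of 0.50 to 0.64 SD (not in the plan), so a margin of 0.25 to 0.32 SD, with zero true difference and 80% power.

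| Margin | n per arm, one-sided 5% | n per arm, one-sided 2.5% |
|---|---|---|
| 0.25 SD | 198.52, so 199 | 252.13, so 253 |
| 0.32 SD | 121.44, so 122 | 154.26, so 155 |

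**Step 4: power that 240 delivers for hypothesis 2.** 240 / 3 = 80 per arm; 80 × 0.85 = 68 completers. One-sided 5%, zero true difference.

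- Adjustment: an assumed baseline correlation r turns the margin into margin / √(1 - r²). The divisor is 0.866 at r = 0.5 and 0.714 at r = 0.7.
- Clustering: design effect 1 + (m - 1) × 0.07, which is 1.63 for groups of 10 and 1.98 for groups of 15. The effective n is 68 / 1.63 = 41.7 or 68 / 1.98 = 34.3. The 0.07 is the top of the stated range ("two recent mindfulness multi-site studies ranged from 0 to 0.07"). The plan does not say that it applies to therapy groups; that is an assumption here.

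| Margin | Unadjusted, no clustering | r = 0.5 to 0.7, no clustering | ICC 0.07, groups of 15 to 10, unadjusted |
|---|---|---|---|
| 0.25 SD | 42% | 51 to 65% | 27 to 30% |
| 0.32 SD | 58% | 69 to 83% | 37 to 42% |
| 0.50 SD | 90% | 96 to 99% | 66 to 73% |

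**Step 5: if a non-significant contrast were read as non-inferiority.** This is the chance of a non-significant two-sided 5% contrast when MBI is truly worse by exactly the margin, with 68 per arm and no clustering.

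| True deficit | Unadjusted | r = 0.5 to 0.7 |
|---|---|---|
| 0.25 SD | 70% | 61 to 47% |
| 0.32 SD | 54% | 43 to 26% |
| 0.50 SD | 18% | 8 to 2% |

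A confidence-limit rule at one-sided 5% holds this chance to 5% for whichever margin is prespecified.

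**The case against.** **The 51 may be entirely sound.** It is reproduced by a simple set of inputs, and under them 240 gives about 90% power before clustering. This stands. A reader might infer that 51 is a calculation error, but the documents do not support that. Nor do they let a reader deduce the margin, or firm limits for it, from the 51: any such range depends on inputs that the reader supplies.

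**The harm in step 5 is conditional.** A reader might infer that the investigators will treat a null ANOVA contrast as non-inferiority. No passage says so. Research question 2 speaks only of comparing effects, which a pairwise comparison does address. This also stands: the step 5 figures show what the missing rule would prevent, not what the plan commits to. It does not explain why the hypothesis was sized for non-inferiority if none was to be tested.

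**The low power figures rest on assumptions.** The 0.25 and 0.32 SD margins need a psychoeducation effect that the plan does not give. The planned baseline adjustment raises power and clustering lowers it, so the net direction is not settled. If all 80 per arm contributed outcomes under intention-to-treat, the unadjusted 42% and 58% would become 47% and 64%.

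**The total is not driven by this calculation.** A reader might infer that the trial as a whole is undersized. This point does not show that: the 240 was built on the larger 64 per arm, and MBI versus usual care does not depend on the margin.

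A figure under Data Analyses is not reproduced in the text available here. The analysis paragraphs that follow it are present and contain no non-inferiority rule.

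**Conclusion.** The concern holds, limited to MBI versus psychoeducation. The planned analysis does not match the hypothesis that was sized: followed exactly, it would never test non-inferiority. The margin lacks a base, an outcome, a time point, an alpha and a reference effect. These two conclusions need no assumed figure beyond taking the second hypothesis to be research question 2.

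The size depends on what the margin turns out to be. At 0.50 SD the sample is adequate before clustering, but half preserved would be the wrong description unless psychoeducation has an effect of about 1.0 SD. At 0.25 to 0.32 SD, 51 per arm falls well short of the 199 to 122 needed at one-sided 5% with zero true difference and no adjustment.

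This should be fixed, but it does not threaten the trial's total or the comparison of MBI with usual care.

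**What to change.** 1. **Add a decision rule before outcomes are seen by arm.** Claim non-inferiority only if the confidence limit for the baseline-adjusted MBI minus psychoeducation difference lies inside the margin, on one named outcome, at one named time point (T1 or T2) and at a stated one-sided alpha. Otherwise report the estimate and its interval, and make no non-inferiority claim.
2. **Define the margin.** Give it in SD or scale units, with the reference effect it derives from and the reason that effect applies to the modified programme. Do not describe 0.50 SD as preserving half of the effect unless a psychoeducation effect of about 1.0 SD is supported.
3. **Restate the numbers.** Confirm or replace 51 per arm under those inputs, and give the power that 240 delivers for hypothesis 2 after drop-out, clustering and baseline adjustment. State the level at which the ICC applies.

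The cost is protocol and SAP wording plus one confidence-limit rule, with no added participants or visits. The downside is that the stated power for hypothesis 2 may become less favourable.

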The research project will be announced and promoted among collaborating NGOs and through advertisement in social media, promotional emails, and project leaflets. Four NGOs have indicated their intentions to contribute to this study by assisting in promotion, recruitment, program implementation and data collection. Support letters of these NGO collaborators have been provided in the appendix.

We will organize briefing sessions for explaining the rationale and procedures of the study half yearly. All interested caregivers will be screened using Clinical Frailty Scale, Clinical Dementia Rating Scale, and caregiver stress. Written consent will be collected for eligible participants. All NGO collaborators will provide standard care to the participants, including participants in Arm 3 who will not receive MBI nor psychoeducation before T2. The Research Assistant who is blinded to the personal data of the participants, will administer the random assignment using computer generated programming. Participants will be randomly assigned to MBI (Arm 1), psychoeducation (Arm 2), or treatment-as-usual (Arm 3). During the recruitment and implementation, both arm 1 and 2 are called "Family Psychoeducation Program", and the term "mindfulness" will not be used for Arm 1 to minimize the potential placebo effect. Cash remuneration coupons will be provided to caregivers who can complete the study at T1 and T2. A recruitment flowchart is attached in Appendix 1.

Procedures

Program planning and training. The themes and content of arms 1 and 2 are summarized in Appendix 2.

MBI (Arm 1). Based on the protocols of PI's previous clinical trials, brief mindfulness exercises will be integrated with psychoeducation of caregiving for frail elderly. The protocol for Arm 1 has been developed on mid-Sept, 2019 for the first pilot study.

Psychoeducation.

(Arm 2). The research team will modify START (STrAtegies for RelaTives) program for

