caregivers of dementia (Livingstone et al., 2014) into a 10-hour group program. Major changes include the content originally related to the caregiving needs of dementia will changed to frail elderly. Two hours will be added to allow for more discussion of individual caregiver's concerns. The protocol for Arm 2 will be developed and a pilot study will be conducted shortly in early 2020. Arm 1 and 2 are parallel in program design. Both will be 4-session programs to be organized bi-weekly, and last for 10 hours in total. Both programs include 15-minute daily home practice assignments, with Arm 1 being guided with mindfulness exercises, and Arm 2 with coping and problem-solving skills. Both arms will be delivered in group format, with 10 to 15 caregivers in each group. Programs will be conducted in the service units of four NGO collaborators and PI's university. All instructors for Arm 1 require basic professional training in MBI, plus at least two-year experience in conducting MBI. Instructors for Arm 2 will be recruited from NGO with experience in working with caregivers of frail elderly for more than two years. Implementation and assessment.

After the pre-intervention assessment (T0), caregivers who meet inclusion criteria will be randomized into a MBI (Arm 1), psychoeducation (PSY, Arm 2), or treatment-as-usual (TAU, Arm 3). After the intervention programs, participants in three arms will complete the post-intervention assessment (T1). A 6-month follow up (T2) is offered as a booster and final assessment for arms 1 and 2. This study will be single-blinded and outcome assessors will be blinded to randomization status.

To ensure intervention fidelity, all program sessions will be audio-recorded and an independent rater will listen to 20% of the selected clips on random basis, and assess whether each element in the intervention protocol has been implemented with consistency. Higher concordance rates will signify greater fidelity to the intervention protocol, which will be carefully monitored throughout the study. The treatment fidelity of Arm 1 will be further assessed by Mindfulness-based Interventions-Teaching Assessment Criteria Scale (Crane et al., 2013). Those of Arm 2 will be assessed by a checklist for implementing START program.

Table 1. Outcome variables and measures

Study variables and measures	Validation in HK samples
Primary outcome variables	

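### After drop-out, 240 leaves a factor of only 1.06 for the stated ICC of 0.07; if that is a treatment-group ICC, 80% power is not shown, and the planned analysis has no term for the groups

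*Combined protocol and SAP*

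**What the plan says.** All references are to the combined protocol and SAP.

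- **Sample size estimation, hypothesis 1.** The effect sizes are 0.64 (depression, from an earlier MBI study) and 0.14 for Arm 3, with a two-sided 5% level: "an 80% power, and a test of three independent groups, the required sample size will be 64 per arm".
- **Sample size estimation, hypothesis 2.** "A non-inferiority margin of 50%, as common practice in non-inferiority trials" "is selected and the required sample size will be 51 per arm". The larger of the two sizes is carried forward.
- **Inflation.** "We further adjust the sample size based on an estimation of drop-out rate and intra-class correlation". Drop-out is put at 15%. The ICC is put at 0.07, taken from "two recent mindfulness multi-site studies ranged from 0 to 0.07". The result is "and 240 caregivers will be recruited for this study".
- **Procedures, on Arms 1 and 2.** "Both arms will be delivered in group format, with 10 to 15 caregivers in each group". Arm 3 receives standard care and attends no programme group before T2 (Recruitment of participants).
- **Study design and 3. Data Analyses.** The analysis is a repeated measures ANOVA. Between-group comparisons are adjusted for baseline scores, age, sex, severity and frailty. Treatment group, instructor and site do not appear.

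**The concern.** Caregivers who attend the same group share an instructor and each other's company, so their outcomes may be correlated. The plan says that 240 already allows for an ICC, but the step from 64 per arm to 240 is not shown, and the room left after drop-out is small for groups of this size. The ICC is also not said to belong to a site or to a treatment group.

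Two things are at stake. The stated 80% power may not hold for a test that respects the grouping. And the analysis as written may give too many false positives, because it treats members of a group as independent.

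**Working it through.** **Inputs.** From Sample size estimation: 64 and 51 per arm, effect sizes 0.64 and 0.14, two-sided 5%, 80% power, drop-out 15%, ICC 0.07 (range 0 to 0.07), total 240. From Procedures: groups of 10 to 15 in Arms 1 and 2. Assumed: equal allocation, since no ratio is stated; d = 0.64 − 0.14 = 0.50, which is inferred.

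**1. Reproducing 64.** A two-sample t-test with d = 0.50, two-sided 5% and n = 64 has power 0.801. The 64 is sound, and the inferred d fits.

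**2. From 64 to 240.** Drop-out alone gives 64/0.85 = 75.3 per arm, 226 in total. Going the other way, 240/3 = 80 per arm and 80 × 0.85 = 68 completers. The factor left for the ICC is 68/64 = 1.0625. Multiplying by 1 + ICC comes close: 3 × 64 × 1.07/0.85 = 241.7. That is the design effect for clusters of two. The plan shows no formula, so this route is only a guess.

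**3. Cluster size that the factor covers.** With design effect DE = 1 + (m − 1) × ICC in both arms, m = 1 + 0.0625/0.07 = 1.9. If only the MBI arm is clustered, the average factor is (1 + DE)/2, so m = 1 + 0.125/0.07 = 2.8.

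**4. Cluster size that the plan implies.** 80/15 = 5.3, so at least 6 groups per arm; 80/10 = 8, so at most 8. Completers per group are 68/8 = 8.5 to 68/6 = 11.3.

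- DE in a clustered arm: 1 + 7.5 × 0.07 = 1.53 to 1 + 10.33 × 0.07 = 1.72.
- Averaged over MBI and the unclustered Arm 3: (1 + 1.525)/2 = 1.26 to (1 + 1.723)/2 = 1.36. Both exceed 1.06.
- For MBI vs TAU, 1.06 is enough only if the group ICC is at most 0.125/10.33 = 0.012 to 0.125/7.5 = 0.017.
- For non-inferiority, where both arms are clustered, the room is 68/51 = 1.33, still below 1.53.

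**5. MBI vs TAU with 68 completers per arm, d = 0.50, ICC 0.07, no baseline gain.** The first row uses a noncentral t with n = 68/[(1 + DE)/2]. The next two use simulation (40,000 runs, 6 to 8 groups, simple comparison of arms at one time point).

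| Test | Power or rejection at d = 0.50 | Two-sided type I error |
|---|---|---|
| Groups accounted for, individual-level degrees of freedom | 70–73% | not simulated (nominal 5%) |
| Group-level test, Satterthwaite degrees of freedom | 63–69% | about 5% |
| Groups ignored | 79–80% | about 8–10% |
| ICC = 0, for reference | 82% | 5% |

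**6. What would narrow the gap.** Baseline adjustment multiplies the variance by 1 − r². A baseline correlation r of about 0.40 (8 groups) to 0.47 (6 groups) brings the 70–73% back to 80%. Halving the ICC to 0.035 gives DE = 1.26 to 1.36, an average of 1.13 to 1.18, and power of about 76 to 78%.

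**7. Detectable difference.** At 80% power vs TAU, by the method of the first row, it is 0.54 to 0.57 SD, against 0.48 at ICC = 0.

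**The case against.** The strongest reply is that 0.07 comes from multi-site studies and is never called a treatment-group ICC. The trial is itself multi-site and randomises individuals, so a site ICC is at least as natural a reading. If randomisation is also within site (not stated), the design effect above does not apply. That stands, and it is why the power figures are conditional. It does not settle the matter. A site ICC says nothing about correlation within treatment groups, so on that reading the group ICC is unknown and nothing is shown to be allowed for it. A reader might infer that no allowance is then needed; the documents do not support that either.

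Three further points also stand in part.

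- 0.07 is the top of the stated range, and an ICC near zero would leave power at about 82%.
- Baseline adjustment is planned and could restore 80% in the 70–73% case. No correlation is stated, though, and the sample size takes no credit for one. Nor does a baseline covariate by itself model correlation that arises within the groups.
- For the analysis as written, the harm is in the false-positive rate; rejection at d = 0.50 stays near 80%.

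A reader might also apply DE = 1 + 14 × 0.07 = 1.98, taking 15 analysed members per group. That cannot happen on average with 68 completers out of 80 in groups of at most 15, so the lower power and higher error rates that follow from it should not be used.

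**Conclusion.** The point holds in conditional form. The plan does not show how 240 was reached or what the ICC refers to. If 0.07 is a treatment-group ICC, the room left for it (1.06) is below what the planned groups need (1.26 to 1.36 for MBI vs TAU). The analysis as written would then have a type I error of about 8 to 10% for that comparison. A test that accounts for groups would have power of about 70 to 73%, or 63 to 69% with group-based degrees of freedom. These figures assume equal allocation, 68 completers per arm, d = 0.50 and no gain from baseline adjustment. The error rate comes from a simple two-arm test, not from the full repeated measures model.

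It would go too far to conclude that the trial is underpowered or that 240 must be raised. The ICC level, its value in this trial and the baseline correlation are all open, so the supported statement is that 80% is not shown. No power figure is given here for non-inferiority, because the 50% margin has no stated scale and that test has no stated alpha.

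**What to change.** Keep 240.

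1. **3. Data Analyses.** Account for treatment group in Arms 1 and 2, for example with a partially nested mixed model: random group effect, small-sample degrees of freedom, Arm 3 unclustered, baseline score as covariate. Record which group each participant attends.
2. **Sample size estimation.** State the ICC level, the group size, the allocation ratio and how 240 was reached.
   - If it is a group ICC, replace the 80% claim by: *With 68 completers per arm, group ICC 0.07, 6–8 groups per arm and no gain assumed from baseline adjustment, power for MBI vs TAU (d = 0.50, two-sided 5%) is about 70–73%, or 63–69% with degrees of freedom based on the groups; with ICC = 0 it is about 82%.*
   - If it is a site ICC, say so, and state that no allowance is made for treatment groups.
3. **Non-inferiority.** Define the margin scale and alpha, then restate its power.
4. **Outcome.** Label the calculation as based on depression, which Table 1 lists as secondary. For the ZBI, the primary outcome, give the detectable difference vs TAU as 0.54–0.57 SD if the same ICC is assumed (0.48 SD at ICC = 0).

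The cost is a less favourable stated power and slightly more analysis work. No extra participants are needed.
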